### 7.0 Multisite -N/A

# **8.0** Study Timelines

- Phase 1: The total duration of an individual's participation in the study is no more than 1.5 hours. The number of study visits is 1 per participant. No follow-up is included in the study. It is anticipated that it will take approximately 10 minutes to consent each participant. The estimated date of completion for this phase of the study (focus group phase) and primary analyses is March 30, 2022.
- Phase 2: The total composite time duration of an individual's participation in the study is estimated to be about 60 minutes. The number of study visits is 3 per participant. All study "visits" are in the form of online survey and video viewing. The first study visit will consist of consenting via cover letter and pre-test. The second study visit will consist of a 1 month-follow-up survey video podcast viewing. The third study visit will consist of a short follow-up survey 3 months following post-test completion. It is anticipated that it will

take approximately 5 minutes to recruit/enroll each participant; 15 minutes to complete the pre-test; 20 minutes to watch draft podcast video; 15 minutes to complete the posttest; and 5 minutes to complete the 3-month follow-up. The estimated date of completion for this phase of the study and primary analyses is August 30, 2023.

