Phase 2: Participants will email or call a dedicated study email/phone line, where research assistants will screen them, answer any questions they may have, and get them formally enrolled, if applicable. Participants will be given a unique ID number. Participants will be emailed a secure unique link to the pre-test survey (which will include cover letter consent information – See Section 22.1). Participants will complete the pre-test measure. One month after pre-test survey completion, participants will be emailed a secure unique line to the post-test survey in which they will view the podcast video and complete the post-test measures. Participants will be emailed a secure unique link 3 months later to complete a brief behavioral outcome questionnaire. The research team will be knowledgeable about the podcasting software in order to assist participants in trouble-shooting, if necessary. Dark Light Studios will also provide consulting throughout the entire research process, if needed. Upon pre-test completion, participants will be emailed (or pick up in person) a \$20 Walmart, Target, or Amazon gift card; \$80 Walmart, Target, or Amazon gift card upon post-test completion; and \$25 Walmart, Target, or Amazon gift card upon 3 month follow-up completion; for an opportunity to receive \$125 for complete participation. For participants who do not have email addresses, research assistants will assist them in obtaining one, within the recruitment procedures, if desired; alternately, participants will be able to schedule a time to meet at one of the community centers in order to complete pre- and post-test surveys in person, and/or to pick up gift card, if needed.

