# [Eligibility Screening Script and Focus Group Script are attached in SmartForms]

Phase 2 – Survey Data: Demographics will include age, biological sex, education, and income. Based upon the behavioral outcomes we expect participants to adopt from the HIV prevention podcasts, we will inquire (pre, 1 mo post, & 3mo): (1) frequency of penetrative sexual intercourse acts in the past month, (2) unprotected penetrative sexual intercourse in the past month, (3) number of sexual partners in

the past month, (4) PhenXToolkit Self-reported HIV Results, and (5) condom use during the last act of penetrative sexual intercourse. Based on the knowledge and psychosocial cognitions we expect to influence, measures (pre & post) will consist of (1) Motivations to use condoms scale, (2) HIV knowledge, (3) attitudes toward condom use, (4) condom use self-efficacy, and (5) condom use communication, (6) perceived social and subjective norms, (7) feedback concerning HIV prevention video content and presentation (1 mo post only), and (8) Marlowe-Crowne social desirability scale(1 mo post only). [A copy of the survey measures is attached in the SmartForm section]

10.4 1 month and 3 month follow-up data will be collected from Phase 2 participants. No follow-up data will be collected form Phase 1 participants.

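### The one-month behavioural items are answered at the visit where the video is first shown, so they describe time before exposure and cannot serve as a podcast outcome

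*Combined protocol and SAP*

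**What the plan says.** Section 8.0 gives three Phase 2 visits. Of the first it says: "The first study visit will consist of consenting via cover letter and pre-test". No viewing is listed there. The second combines the one-month survey with the video, and the third is a short survey 3 months after the post-test.

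Section 10.2 gives the same order. "One month after pre-test survey completion, participants will be emailed a secure unique line to the post-test survey", and that link opens the "post-test survey in which they will view the podcast video and complete the post-test measures". Then: "Participants will be emailed a secure unique link 3 months later to complete a brief behavioral outcome questionnaire".

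Section 10.3 sets the behavioural items at three occasions: for the "behavioral outcomes we expect participants to adopt from the HIV prevention podcasts, we will inquire (pre, 1 mo post, & 3mo"). The first two are "1) frequency of penetrative sexual intercourse acts in the past month, (2) unprotected penetrative sexual intercourse in the past month". The others are number of partners (also past-month), self-reported HIV results, and condom use at the last act. The psychosocial scales have their own schedule: "Based on the knowledge and psychosocial cognitions we expect to influence, measures (pre & post) will consist of" motivation, knowledge, attitude, self-efficacy, communication and norm measures. Section 10.4 adds: "1 month and 3 month follow-up data will be collected from Phase 2 participants".

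For analysis, 10.1 refers to repeated measures analyses with N=128, and 25.1 plans repeated measures t-tests on the variables of interest. Neither names the occasions to be compared.

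**The concern.** A behavioural outcome can reflect an intervention only if the period it describes falls after the intervention. Section 10.3 presents the one-month behavioural answers as something participants are expected to take from the podcasts, and 10.4 calls that visit follow-up. The schedule in 8.0 and 10.2 puts the first viewing at that same visit.

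A paired t-test compares two occasions. With three behavioural occasions there are three possible pairs, and pre-test versus one month is one of them. Its label makes it look like the first outcome, but both of its values describe unexposed time. A difference could arise from time trend, from having answered the survey before, or, if the items follow the video, from a change in how people report just after watching it. None of these is a behavioural effect of the podcast. Equally, no difference would say nothing about whether the podcast works. Aim 2 is to evaluate effectiveness, so a result attributed to the podcast on this comparison would go to the centre of the study's claim.

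**Working it through.** **1. Is there one viewing, at visit 2, and no separate survey a month after it?**

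- Section 8.0 itemises time per participant: 5 (enrolment) + 15 (pre-test) + 20 (video) + 15 (post-test) + 5 (3-month survey) = 60 minutes. This reproduces the stated total of about 60. With no viewing the sum would be 60 − 20 = 40, with two viewings 60 + 20 = 80, and with a second post-test 60 + 15 = 75.
- Section 17.2 pays for three survey activities: \$20 + \$80 + \$25 = \$125, which is the stated maximum. There is no fourth payment.
- Section 8.0 states three visits and itself calls the viewing visit the one-month follow-up.
- Section 10.3 collects feedback on the video only at the occasion it labels one month post. That fits the visit at which the video is shown.

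All four point the same way: the one-month post occasion is visit 2, and no other survey is scheduled until 3 months later.

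**2. How much of each recall window follows viewing?**

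Assumptions: a month is 30 days; the visit-2 measures are answered in the same sitting as the video. From 8.0 and 10.2, the pre-test is at day 0, viewing at day V = 30 and the post-test at day 30, and the last survey is at day 30 + 90 = 120. For a survey on day S with 30-day recall,

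days after exposure = max(0, S − max(S − 30, V)).

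| Survey | S | Recall window (days) | Days after viewing |
|---|---|---|---|
| Pre-test | 0 | −30 to 0 | 0 of 30 |
| One month post (visit 2) | 30 | 0 to 30 | 30 − max(0, 30) = 0 of 30 |
| 3 months | 120 | 90 to 120 | 120 − max(90, 30) = 30 of 30 |

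If someone paused 1 to 7 days between video and measures, which the protocol does not describe, 1/30 = 3% to 7/30 = 23% of the window would follow viewing.

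**3. Items without a fixed window.** Last-act condom use and self-reported HIV results, answered in the same sitting as the video, can also only report earlier events.

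**4. Does item order matter?** The survey instrument is an attachment and was not available. Whether the behavioural items come before or after the video, the behaviour described precedes viewing. Order affects only whether the reporting could be influenced by the video.

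**5. Is the comparison in the plan?** Section 10.3 makes these items study variables at three occasions. Section 25.1 applies repeated measures t-tests to the study variables and excludes no occasion. The comparison is permitted but not named.

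**The case against.** The strongest reply is that the protocol never states a pre-test versus one-month behavioural test, so the fault is inferred from silence. Section 10.2 reserves the name behavioural outcome questionnaire for the 3-month survey, and 9.1 ties the primary endpoint to 3 months after the last post-test. This stands in part. The comparison is indeed not named. But 9.1 reads as a completion date and names no outcome, and 10.3 explicitly lists the one-month answers among the outcomes expected from the podcasts. Nothing marks them as a second baseline.

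A second reply is that the behavioural evaluation survives. This stands. A reader might infer that Phase 2 cannot assess behaviour at all. The documents do not support that: the 3-month window lies wholly after viewing and can be compared with either earlier survey. Nor are the knowledge and cognition scales void for this reason. They can change straight after viewing, although their change also spans the untreated month.

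A reader might also infer that any conclusion from the one-month comparison would be false. That goes too far: such a conclusion would be unsupported, but it could happen to be true.

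Finally, one might want to size the fault as a false-positive rate. That would need an assumed drift in untreated behaviour, which the documents do not give. It would also apply to any uncontrolled pre-post comparison, including one that uses the 3-month survey, so it would not measure this fault.

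**Conclusion.** The point holds and should be fixed. As written, none of the roughly 30 recall days in the one-month behavioural items follows viewing, and the two items without a recall window also look back from the same sitting. A pre-test versus one-month behavioural comparison therefore cannot contain a podcast effect on behaviour at any sample size, yet the plan labels that occasion as an outcome and leaves the comparison open.

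This rests on the sequence in 8.0 and 10.2, on a 30-day month, and on video and measures being completed together. A pause of a few days would change the figure only slightly. It does not depend on item order. It is limited to the behavioural items at visit 2. The 3-month behavioural measurement is intact, but with no control group it remains open to time trend, which is a separate limitation.

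A reader might take the one-month label to mean that a survey a month after viewing was intended and left out. The visit count, payments and time total give no support to that. Only the sponsor can confirm what was meant.

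**What to change.** First confirm that the sequence in 8.0 and 10.2 is the intended one.

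**If it is:**

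- In 10.2 to 10.4, state that the visit-2 behavioural items are asked before the video and are a second pre-exposure measure. Relabel the occasions relative to viewing: one month before, at viewing, 3 months after.
- In 25.1, name the behavioural comparison as the 3-month value against one pre-specified pre-exposure value. Use visit 2 if its items precede the video. Otherwise use the pre-test, because visit-2 reporting could be influenced by the video.
- Report behavioural change from pre-test to visit 2 only as change over an untreated period.

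The cost is protocol and analysis wording and possibly survey item order, submitted to the IRB, with no extra participants, visits or payments. If the attached survey already puts these items before the video, only labels and analysis text change. The downside is that one fewer occasion counts as a behavioural outcome, and the visit-2 survey may have to be split around the video.

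**If a survey one month after viewing was intended:** relabelling does not solve the problem. Sections 8.0, 10.2 to 10.4 and 17.2 must be reconciled, because the visits, minutes and payments contain no such survey, and its cost is not budgeted in the documents.

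### As most naturally read, the plan collects past-month behaviour at visit 2 after the HIV video; those items should come before it, and section 10.2 should say so

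*Combined protocol and SAP*

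**What the plan says.** **Timing and order.** Section 10.2 (Phase 2) states: "One month after pre-test survey completion, participants will be emailed a secure unique line to the post-test survey". It describes that survey as one "in which they will view the podcast video and complete the post-test measures". Section 8.0 budgets "20 minutes to watch draft podcast video; 15 minutes to complete the posttest", in that sequence. Another sentence in section 8.0 is less clear and names the survey before the viewing: "The second study visit will consist of a 1 month-follow-up survey video podcast viewing".

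**Content.** For the behavioural outcomes, section 10.3 says "we will inquire (pre, 1 mo post, & 3mo): (1) frequency of penetrative sexual intercourse acts in the past month". The list continues with "unprotected penetrative sexual intercourse in the past month", the number of partners over the same window, the self-reported HIV result, and "condom use during the last act of penetrative sexual intercourse". The knowledge and condom-cognition scales are given at pre-test and post-test. The video feedback and the social desirability scale are given at one month only. The survey itself is an attachment and is not shown.

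**Analysis.** Section 10.1 describes a repeated-measures design with N=128, and section 25.1 plans paired t-tests on the study variables. No control group is described. No contrasts, significance level or use of the social desirability scale are stated.

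**The concern.** The same behaviour items appear to be asked under different conditions. At pre-test nothing precedes them. At visit 2 they appear to follow, within minutes, a message about what participants ought to be doing. The month being recalled is already over by then, and if video and survey are done in one sitting, so is the last act. The video cannot have changed that behaviour, but it can change what people are willing to report about it.

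A shift in reporting would look like a change in behaviour in a paired comparison of pre-test with visit 2, and there is no control group to reveal it. The social desirability scale cannot separate the two, because it is given once, at this visit, and has no stated role in the analysis.

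This is separate from the question of which month visit 2 describes. Treating visit 2 as a second pre-video measurement does not free its answers from the video if they are given after it.

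**Working it through.** **1. Order, from the texts side by side.**
- Section 10.2: video and post-test measures share one link, with the video named first. The joining word is *and*, not *then*.
- Section 8.0, time budget: video (20 minutes), then post-test (15 minutes).
- Section 8.0, visit description: survey named before viewing, in a garbled sentence that fixes no order.
- Section 10.3: behaviour items belong to the one-month survey; their position relative to the video is not given.

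Two of these favour video first, one is ambiguous and one is silent. None places the behaviour items before the video.

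**2. Which comparisons are affected.** Suppose that visit-2 reports are shifted by an amount *b* towards safer behaviour and that nothing else changes.
- Pre-test to visit 2: biased by *b* towards benefit.
- Visit 2 to 3 months: biased by *b* against benefit, because the reference already looks safer than it was.
- Pre-test to 3 months: visit 2 does not enter, so this bias is zero.

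**3. How large a shift would matter.** The documents give no size for *b*, so a range is assumed. Other assumptions are two-sided 5% (not stated in the plan), no true change and no dropout. The sample sizes are 128 (section 5.3) and 64 for one sex. With *d* = *b* divided by the SD of the paired differences, the paired t statistic is noncentral t with n − 1 degrees of freedom and noncentrality *d*√n, where √128 = 11.314 and √64 = 8. The probability is that of rejection in either direction.

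| *d* (assumed) | *d*√128 | P(significant), n=128 | *d*√64 | P(significant), n=64 |
|---|---|---|---|---|
| 0 | 0 | 5% | 0 | 5% |
| 0.10 | 1.131 | 20% | 0.80 | 12% |
| 0.20 | 2.263 | 61% | 1.60 | 35% |
| 0.25 | 2.828 | 80% | 2.00 | 50% |

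The smallest observed shift that reaches p<0.05 is the critical t divided by √n: 1.979/11.314 = 0.175 SD at n=128, and 1.998/8 = 0.25 SD at n=64.

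**4. Participant time.** The plan's total reproduces: 5 + 15 + 20 + 15 + 5 = 60 minutes, of which visit 2 takes 20 + 15 = 35. Reordering changes neither figure. With the behaviour items before the video, *b* from this source is zero by design, and the rejection probability returns to the assumed 5%.

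**The case against.** **The order is not stated.** This stands in part. A reader might infer that the plan fixes video first, item by item. It does not: the wording is loose, one sentence points the other way, and the unseen instrument may already ask behaviour first. Video first is still the more natural reading, and if the instrument does ask behaviour first, the edit merely records it.

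**The probabilities say nothing specific to this trial.** This stands. They are the power curve of a paired t-test at assumed shifts with full return at one month. They show that a modest shift would matter, not that one is likely.

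**The 3-month result is safe.** This stands for the comparison with pre-test, and section 9.1 places the primary endpoint at 3 months after post-test. A reader might infer that the item order undermines that endpoint. The documents do not support this, because they name no contrast that uses visit 2 as the reference, and section 10.3 labels visit 2 as post. The second bias in the working arises only if such a contrast is chosen.

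**A larger problem comes first.** The month recalled at visit 2 precedes the video whatever the item order, and the one-month labels may have been meant to count from the viewing. If the schedule were clarified so that the survey followed the video by a month, the order question would disappear. The fix is therefore conditional on the video staying at visit 2.

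**The change is not free.** This stands. Behaviour items asked just before the video could prime the viewing and the scales that follow. The effect should be slight, since the pre-test already asks the same items.

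**Conclusion.** The concern holds as a should-fix, with medium confidence. On the natural reading, visit-2 behaviour reports follow a video that the reported month preceded, while pre-test reports do not. A shift towards safer reports would bias pre-test to visit 2 towards apparent benefit. It would tend to hide benefit in any visit-2 to 3-month contrast, and it leaves pre-test to 3 months untouched.

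Both the size and the direction of the shift are assumptions. The 20%, 61% and 80% (12%, 35% and 50% for one sex) are illustrations, not estimates of this trial's false-positive rate.

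A reader might also infer that reordering turns visit-2 behaviour into an outcome of the video. It does not: visit 2 remains a second pre-video measurement. Nor does reordering remove any social desirability bias in the 3-month reports.

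**What to change.** If the video stays at visit 2, amend section 10.2 to state the order: participants complete the behaviour items (section 10.3, behavioural list, items 1 to 5), then view the video, then complete the knowledge and cognition scales, the video feedback and the social desirability scale. Only the behaviour block moves; the other measures need to stay after the video. Bring the visit-2 sentence in section 8.0 into line and set the online survey to the same order.

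The cost is one survey page reorder, a minor protocol edit with whatever ethics-board handling it requires, and possible slight priming. Items, visits, payments, sample size and the 60-minute total do not change.

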#### 10.3

There will be no drugs, devices, or biologics used in the research.

Eligibility Screening Form/Script: For Phase 1 and 2, the eligibility screening form/script will indicate age, race, preferred language, and Houston residence status (i.e., "Do you currently reside in Houston MSA?").

Phase 1 - Focus Group Script: The focus group script will contain questions that ask about condom use and perceptions of HIV and other STIs. The first part of the discussion will ask about familial and media messages concerning safer sex (35 minutes); the second part will ask about safe sex curriculum materials (25 minutes); and the third part will discuss perceptions about condom use (20 minutes). 10 minutes is allotted for "anything else" participants would like to share.

# [Eligibility Screening Script and Focus Group Script are attached in SmartForms]

Phase 2 – Survey Data: Demographics will include age, biological sex, education, and income. Based upon the behavioral outcomes we expect participants to adopt from the HIV prevention podcasts, we will inquire (pre, 1 mo post, & 3mo): (1) frequency of penetrative sexual intercourse acts in the past month, (2) unprotected penetrative sexual intercourse in the past month, (3) number of sexual partners in

the past month, (4) PhenXToolkit Self-reported HIV Results, and (5) condom use during the last act of penetrative sexual intercourse. Based on the knowledge and psychosocial cognitions we expect to influence, measures (pre & post) will consist of (1) Motivations to use condoms scale, (2) HIV knowledge, (3) attitudes toward condom use, (4) condom use self-efficacy, and (5) condom use communication, (6) perceived social and subjective norms, (7) feedback concerning HIV prevention video content and presentation (1 mo post only), and (8) Marlowe-Crowne social desirability scale(1 mo post only). [A copy of the survey measures is attached in the SmartForm section]

10.4 1 month and 3 month follow-up data will be collected from Phase 2 participants. No follow-up data will be collected form Phase 1 participants.

## 11.0 Setting

- 11.1 Phase 1: Research procedures will be performed within a closed-door conference room at a community center in the evenings and/or on Saturdays. Letter of support is attached in Smartforms. Phase 2: Procedures will be performed on participants' individual personal computing device (computer, smart phone, etc.) Participants will have the opportunity to arrange to complete study procedure (survey data collection and podcast viewing) in person, at a designated community center, if needed.
  - There will be no involvement of a community advisory board.
  - The Blacklist Association, MMOA, Action One Media group, and research team will recruit primarily through word-of-mouth and directing community members to check out the IRB-approved study flyers that will posted on community bulletin boards within the Houston MSA. Community bulletin boards at community centers are free to the public. Community centers are available for scheduling usage of closed-door conference areas. [Letters of Support are attached in Smartforms.]

